1.0 Objectives

1.1 Describe the purpose, specific aims, or objectives of this research. Specifically, explain why it is important to do the study.

The purpose of this study is to investigate the effectiveness of rTMS combined with rehabilitation in patients with complex regional pain syndrome type 1 (CRPS). CRPS is associated with pain, disability, psychological distress, and social interference.^{1,2} The disorder is difficult to treat and often leads to long-term problems. Several interventions are recommended including medication, rehabilitation, cognitive/psychological interventions, and invasive pain management devices such as dorsal column root stimulators.³ Despite these interventions, many individuals have persistent pain and disability. Recent studies have investigated rTMS as an intervention for painful conditions that have a poor response to other treatments.^{4,5} These studies suggest that rTMS leads to reduced pain in the short-term. Three studies have used rTMS to treat patients with CRPS with promising short-term results.⁵⁻⁷ There have been no studies looking at the impact of combining rTMS with high-quality rehabilitation. Combining rTMS and high-quality rehabilitation may lead to better short-term and long-term outcomes. The aims of this study are:

1: Determine the short-term effects of rTMS and rehabilitation on pain intensity, pain interference, physical function, fatigue, depression, anxiety, and satisfaction with participation in social roles.

2: Determine the long-term effects of rTMS and rehabilitation on pain intensity, pain interference, physical function, fatigue, depression, anxiety, and satisfaction with participation in social roles.

2. Prasad, MD A, Chakravarthy, MD K. Review of complex regional pain syndrome and the role of

the neuroimmune axis. *Mol Pain*. 2021;17. doi:10.1177/17448069211006617

2.0 Scientific/Safety Endpoints

2.1 *Describe the scientific endpoint(s), the main result or occurrence under study.*

NOTE: Scientific endpoints are outcomes defined before the study begins to determine whether the objectives of the study have been met and to draw conclusions from the data. Include primary and secondary endpoints. Some example endpoints are: reduction of symptoms, improvement in quality of life, or survival. Your response should not be a date.

Endpoints:

- 1- The pilot stage of the project will be complete after 12 subjects or 4 months, whichever comes first. At this point, adjustments will be made to the protocol and recruitment strategies as needed. Any changes will be submitted to the IRB for approval.
- 2- Stage two of the study will continue until a total of 20 subjects have completed the testing, or 30 total subjects have been enrolled. If 30 subjects have been enrolled, but less

than 20 subjects have completed the protocol the authors will re-assess the study methods and consider amending the IRB protocol to include more than 30 subjects.

- 3- The study may be stopped if there is no new enrollment in the study for up to 6-months.
- 4- The study will be stopped after the pilot stage if more than 30% of subjects withdraw from the study due to side effects or excessive burden from the treatment protocol.

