4.0 Study Design

4.1 Describe and explain the study design (e.g. case-control, cross-sectional, experimental, interventional, longitudinal, and observational). Indicate if there is randomization, blinding, control group, etc. If randomizing, explain how this will be achieved. For studies that have a complex study design (i.e., multiple arms and treatments), include a schematic diagram.

This study will have a pilot phase and a randomized phase. The pilot phase will include 1-3 subjects who will receive real rTMS and rehabilitation. Subjects in the placebo controlled randomize phase will receive rehabilitation combined with either real or sham rTMS. Randomization will be performed in REDCap and be stratified by upper or lower extremity. Randomization will occur in blocks of 4 to ensure equal distribution. Patients and the physical therapists delivering rehabilitation will be blinded to group allocation (real/sham rTMS). The researcher administering the rTMS will not be blinded.

Changes included in protocol version 2:

- Addition of new advertisement document that will be handed out by clinicians to potential subjects.
- Addition of a pilot phase that will include 1-3 unrandomized subjects.
- Adjusted the subject numbers to reflect the pilot phase subjects.
- Added [name] to the study team.
- Created new informed consent document for the pilot phase.

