6.0 Local Number of Subjects

6.1 *Indicate the total number of subjects who will be enrolled or records that will be reviewed through Upstate.*

Based on the power analysis and overage for dropouts a maximum of 33 subjects will be enrolled in the study. The goal is to have at least 20 subjects complete all testing.

6.2 *If applicable, indicate your screen failure rate, i.e., how many subjects you expect to screen to reach your target sample.*

We are attempting to keep the inclusion/exclusion criterion broad and we are including patients with upper and lower extremity symptoms. After phase one of this project, we will have a better idea of the screening failure rate. Given the lack of alternative treatments for this condition and the impact symptoms can have on quality of life, we feel that potential subjects will be highly motivated to be involved in the study.

6.3 Justify the feasibility of recruiting the proposed number of eligible subjects within the anticipated recruitment period. For example, how many potential subjects do you have access to? What percentage of those potential subjects do you need to recruit?

Recruitment for this study may be challenging due to the rarity of the condition. We are partnered with the Upstate PM&R department who routinely see patients with this condition. We will also send recruitment materials to pain management specialists and surgeons inside and outside the Upstate system.

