 - Week 3- Mirror therapy (third component of GMI), add meditation, assess knowledge and update education as needed, progress graded activity 1 and 2, and add 3rd graded activity if appropriate based on patient goals.
 - Week 4- Continue with week 3 activities. Discuss experience with meditation and progress graded activity as tolerated.
- Pilot Testing
- This is a new treatment protocol for our lab. To test and adjust the logistics of the protocol 1-3 subjects will be enrolled as pilot subjects. The subjects will complete the standard protocol but will not be randomized. All 1-3 subjects in the pilot testing will receive the real rTMS.

11.1 Describe what data, including long-term follow-up, will be collected.

NOTE: For studies with multiple data collection points or long-term follow up, consider including a schedule or table in your response.

Measurements:

- The first visit
 - All instruments except the GROC
 - Basic demographics and other relevant medical information will be collected at this visit
- The last visit of each week
 - All outcome instruments will be collected
- All outcome instruments will be collected at 4-time points after the termination of the interventions-via REDCap e-mail survey or mailed survey if the subject does not have access to e-mail.
 - 4 weeks
 - 3 months
 - 6 months
 - 1 year

List, and upload, any instruments or measurement tools used to collect data (e.g. survey, scripts, questionnaire, interview guide, validated instrument, data collection form).

All of the listed instruments will be uploaded with this IRB submission.

- Numeric Pain Rating Score (0-10): Weekly average and worst and least pain intensity over past 24 hours
- NIH Patient-Reported Outcomes Measurement Information System (PROMIS): Pain interference, pain behavior, physical functioning, satisfaction with discretionary social activity, satisfaction with social roles, fatigue, depression, anxiety, and anger.
- CRPS Severity Score
- Patient Global Impression of Change (GROC) (only measured at follow-up)- scale rated from -7 (a very great deal worse) to +7 (a very great deal better) with 0 being about the same.
- Patient Acceptable Symptom State (PASS): Considering all the different ways your pain symptoms are affecting you, if you were to stay in this state for the next few months, do you consider that your current state is satisfactory?" (Yes/No)
- Adverse events

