17.0 Provisions to Monitor the Data to Ensure the Safety of Subjects

N/A: This study is not enrolling subjects OR is limited to records review procedures only OR is a minimal risk study

17.1 Describe the plan to evaluate the data periodically regarding both harms and benefits to determine whether subjects remain safe. The plan might include establishing a data safety monitoring committee and a plan for reporting data monitoring committee findings to the IRB and the sponsor.

Subjects will be directly monitored by study personnel during the rTMS and rehabilitation sessions. During rTMS it is expected that some subjects may experience mild headaches, local scalp discomfort, and muscle twitching. Subjects will be consistently monitored and stimulation intensity will be reduced if symptoms are not tolerated or if muscle twitch magnification occurs. During rehabilitation sessions, it is expected that some subjects may experience temporary exacerbation of their normal symptoms. The physical therapist delivering care will monitor subjects and adjust treatment intensity based on the subject's tolerance. Subjects can also request to stop participation in the study at any time for any reason. Study personnel will be in close communication and if the protocol is consistently poorly tolerated by subjects the study will be paused and the protocol will be reviewed and changed as needed.

17.2 Describe what data are reviewed, including safety data, untoward events, and efficacy data.

EMG data and visual observation will be used to assess muscle activation during rTMS. Subject report will be used during rTMS and rehabilitation to monitor response.

17.3 Describe any primary or secondary safety endpoints.

Muscle activity spreading beyond the stimulated area or increasing in magnitude despite lowering stimulation intensity. Unpleasant sensation associated with the interventions that is deemed intolerable or excessive by the subject or research personnel.

17.4 Describe how the safety information will be collected (e.g., with case report forms, at study visits, by telephone calls with participants)

Muscle activation will be recorded via EMG. At the end and beginning (other than the first session) of every rTMS and rehabilitation session subjects will be asked to report any adverse events. This will be recorded on REDCap as either “none” or, if present, the symptoms will be documented.

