24.0 Informed Consent

24.1 Will you be obtaining consent from subjects?

Yes *(If yes, Provide responses to each question in this Section, and upload your consent documents)*

No *(If no, Skip to next section)*

24.2 Describe how the capacity to consent will be assessed for all subjects. (See SOPs, section 14.7.2 for guidance)

The capacity to consent will be assessed during the screening process for all subjects. Subjects will be asked if they have any questions or difficulty understanding the verbal and written communication, and the associated risks of the procedures. If comprehension difficulties are present, further verbal communication will be offered (including reading the consent documents to the subject) by an investigator. Individuals who are not fluent in English will be excluded from the study.

24.3 Describe the consent process that will be conducted to ensure that subject is fully informed regarding study details and subject rights. Include where the consent process will take place, with consideration of the need to protect the subject's right to privacy.

Step 1: During the phone screening process subjects will be asked if they would like a copy of the consent documents e-mailed to them before the first visit. This will be encouraged so subjects have ample time to review the documents. Study procedures will be verbally explained to subjects using a standardized script. Subjects will be encouraged to ask questions about the study. Subjects in the pilot phase will receive a consent document that does not include information about randomization and sham rTMS. The consent document provided to subjects in

the randomized phase of the trial will contain language on the randomization process, sham rTMS, and blinding.

Step 2: During in-person screening study procedures will be verbally explained to subjects using a standardized script. Subjects will be encouraged to ask questions about the study.

Step 3: During the in-person screening potential subjects will be given 2 paper copies of the consent documents. They will be given as much time as needed to review the documents and ask questions. Subjects who agree to participate will keep one copy of the consent documents and provide a signed copy to the investigator.

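### Three enrolment limits (30, 33 and 36) disagree, and the mandatory 30% stop rests on the word pilot, which the protocol uses for two groups of different size

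*Combined protocol and SAP*

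**What the plan says.** **Enrolment.** Section 2.1 item 2 continues the study until 20 subjects have completed testing or 30 in total have been enrolled. If 30 are enrolled with fewer than 20 completers, the methods are reassessed and an amendment to go beyond 30 is considered. Section 6.1 sets a maximum of 33. Section 5.2 allows up to 36. Sections 5.2 and 6.1 both present their figure as the power calculation plus an allowance for dropouts.

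**Pilot.** Section 2.1 item 1 says: "The pilot stage of the project will be complete after 12 subjects or 4 months, whichever comes first". Item 4 of the same list says that the trial "will be stopped after the pilot stage if more than 30% of subjects withdraw from the study due to side effects or excessive burden".

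Section 4.1 describes the structure differently: "This study will have a pilot phase and a randomized phase", and then "The pilot phase will include 1-3 subjects who will receive real rTMS and rehabilitation". Section 11 agrees with 4.1: "To test and adjust the logistics of the protocol 1-3 subjects will be enrolled as pilot subjects", all on real rTMS and not randomised. Section 24.3 adds, without giving a number: "Subjects in the pilot phase will receive a consent document that does not include information about randomization and sham rTMS". Section 6.2 uses a further label that is not defined: "After phase one of this project, we will have a better idea of the screening failure rate".

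**The concern.** A protocol should state one enrolment limit, because that is the number the IRB approves and the team works to. Here a reader of 5.2 would plan for 36, a reader of 6.1 would stop at 33, and a reader of 2.1 would reassess at 30.

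The second matter is a decision threshold. The stop in item 4 is worded as mandatory, and its denominator is given only as subjects at the end of the pilot stage. A pilot of at most 3 subjects can never reach 12, so the two descriptions cannot be the same group, and no section links them. The jobs overlap as well: 2.1 adjusts the protocol after its pilot stage, and section 11 uses its pilot subjects to adjust logistics. Someone working from 4.1 finds one pilot only, and in that group a single withdrawal for side effects or burden is already above 30%. At stake is whether one such early withdrawal ends the trial or has no consequence.

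**Working it through.** **1. The plan's own sample size.** Section 5.2 gives partial eta squared 0.07, effect size f = 0.274, alpha 0.05, power 80%, 2 groups, 4 measurements, correlation 0.5 and nonsphericity 1. For the within-between interaction:

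- f = sqrt(0.07/0.93) = 0.274
- noncentrality = f² × N × m / (1 − rho) = 0.274² × 20 × 4 / 0.5 = 12.0
- degrees of freedom = (2 − 1)(4 − 1) = 3 and (20 − 2)(4 − 1) = 54
- power = 0.811

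The smallest even N that reaches 80% is 20, so the stated figure reproduces.

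**2. Enrolment limits against 20 completers.** Tolerated non-completion = 1 − 20/enrolled:

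- 30 enrolled: 33.3%
- 33 enrolled: 39.4%
- 36 enrolled: 44.4%

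30 + 3 = 33, so 6.1 fits 2.1 plus the largest 1-3 subject pilot. This is an inference. The version 2 change list in 4.1 says that subject numbers were adjusted for the pilot subjects, which is consistent with it but names no figure. No other stated number gives 36.

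**3. Withdrawals needed to stop.** This is the smallest k with k/n > 0.30:

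- n = 1-3: k = 1 (100%, 50%, 33.3%)
- n = 4-6: k = 2
- n = 7-9: k = 3
- n = 10-12: k = 4 (for 12 subjects, 3/12 = 25% does not trigger and 4/12 = 33.3% does)

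**4. Likely size of the item 1 stage.** Section 12.1 anticipates 2 years of enrolment. Assuming an even pace, 30 to 36 subjects over 24 months gives 30 × 4/24 = 5.0 to 36 × 4/24 = 6.0 subjects in 4 months, so the time limit would close the stage before 12 are reached. At the 1-year low end in 12.3, 30 or 33 subjects give 10 or 11.

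**5. Chance of stopping.** This is the binomial P(X ≥ k). The documents give no rate of withdrawal for side effects or burden, so 10% to 40% is assumed.

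| n | k | 10% | 20% | 30% | 40% |
|---|---|---|---|---|---|
| 1 | 1 | 10.0% | 20.0% | 30.0% | 40.0% |
| 2 | 1 | 19.0% | 36.0% | 51.0% | 64.0% |
| 3 | 1 | 27.1% | 48.8% | 65.7% | 78.4% |
| 5 | 2 | 8.1% | 26.3% | 47.2% | 66.3% |
| 6 | 2 | 11.4% | 34.5% | 58.0% | 76.7% |
| 12 | 4 | 2.6% | 20.5% | 50.7% | 77.5% |

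Example, n = 5 at 10%: 1 − 0.9⁵ − 5 × 0.1 × 0.9⁴ = 1 − 0.59049 − 0.32805 = 0.0815.

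At 10%, 3 subjects against 5 or 6 gives 27.1/8.15 = 3.3 or 27.1/11.4 = 2.4. Against 12 it is 0.271/0.0256 = 10.6. With 10 or 11 subjects (k = 4) the chance is 1.3% or 1.9%, and the ratio is about 21 or 15.

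**The case against.** The strongest reply is that the stop rule is defined where it stands. Item 4 uses the term *pilot stage*, and item 1 of the same list defines exactly that term. The 1-3 subject group is called a phase, testing or subjects, never a stage, and the loose label in 6.2 concerns screening failures. This largely stands. A reader might infer that item 4 as written applies to the 1-3 subjects, but the documents do not support that; the item 1 stage is the natural reading. What survives is that 4.1, the section that sets out the design, mentions no other pilot, and nothing tells its reader that item 4 means a different group.

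A reader might also infer a roughly tenfold difference in the chance of stopping. That compares 3 subjects with a full 12 at a 10% rate, and the anticipated 2-year accrual would probably close the stage at 5-6 subjects, where the ratio is 2.4 to 3.3. At 10%, the ratio for 3 subjects runs from about 2 to 21 as accrual pace varies. With a single pilot subject the chance is 10%, about the same as with 5-6. At a 40% rate, 3 and 12 subjects barely differ. No one figure should be quoted alone.

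On enrolment, it is fair to say that 33 and 36 are ceilings, that 33 satisfies both, and that the reassessment at 30 limits the practical effect. The three statements still need to agree.

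**Conclusion.** The point holds as two internal inconsistencies that should be corrected. Three enrolment limits are stated; 33 can be reconciled with 30 if up to 3 pilot subjects are added, and 36 cannot be reconciled with anything stated. The tolerated non-completion they imply runs from 33% to 44%. Separately, a mandatory stop rests on a word used for two groups. At an assumed 10% withdrawal rate the chance of stopping is 10-27% with 1-3 subjects, against 2.6% with 12 or about 8-11% with 5-6. These figures rest on assumed rates and, for 5-6, on even 2-year accrual. How likely a misreading is cannot be estimated.

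Two stronger inferences are not supported. The ambiguity does not leave harm unmonitored: under 17.1, "if the protocol is consistently poorly tolerated by subjects the study will be paused and the protocol will be reviewed and changed as needed", and 17.7 requires safety meetings at least every 3 months. The main risk is ending a tolerable protocol by mistake. Nor is the power calculation undermined: 20 reproduces, and the randomisation and primary endpoint are not touched.

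**What to change.** 1. **Section 5.2:** change 36 to 33, once the sponsor confirms that 33 means 30 plus up to 3.
2. **Section 2.1 item 2:** replace the limit of 30 in total with 30 randomised subjects plus up to 3 run-in subjects; otherwise it would still conflict with 33. Say whether run-in subjects count toward the 20 completers. The calculation assumes 10 per randomised group, and counting 3 unrandomised subjects would leave 20 − 3 = 17 randomised completers.
3. **Section 2.1 item 4:** state that the rule applies to the item 1 pilot stage, with more than 30% of those enrolled as the trigger: 4 of 12, or, if 4 months comes first, 2 of 4-6, 3 of 7-9 or 4 of 10-11. State that it does not apply to the 1-3 subject group alone, and whether those subjects count among the 12.
4. **Sections 4.1, 11 and 24.3:** rename the 1-3 subject group *logistics run-in*.

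The cost is wording in these sections and one IRB amendment.

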3.0 Background

3.1 Provide the scientific or scholarly background, rationale, and significance of the research based on the existing literature and how it will contribute/fill in gaps to existing knowledge.

Complex regional pain syndrome type 1 is a chronic condition that includes sensory, motor, vasomotor, autonomic, and tissue dysfunction.^{1,2} Symptoms include pain, swelling, stiffness, weakness, and skin changes.³ The disorder primarily impacts the extremities with 59% of the cases involving the upper extremity.² The precise incidence rate is unclear and has been reported to be between 2.16-40.4 per 100,000 person years.²⁴ CRPS impacts women 4 times more than men and the most common precipitating event is a fracture.^{4,5} The long-term impact of CRPS is uncertain and it is common for individuals to have long-lasting symptoms. Sandroni et al identified 74 cases of CRPS in Olmsted County (Minnesota, population of 106,470) and found a resolution rate of 74% with a range of 1-60 months.⁴ In contrast, Schwartzman et al looked at 656 patients with CRPS of at least 1-year and found a 0% resolutions rate.³ This suggests that CRPS symptoms lasting more than a year are unlikely to resolve.

Literature on the effectiveness of treatments for patients with CRPS is limited and often of low quality. Systematic reviews and guidelines support the use of education, medication, and rehabilitation involving graded motor imagery as first-line interventions.^{1,6,7} These interventions appear to be effective for some individuals, but effect sizes are small and they do not provide a meaningful reduction in symptoms for a significant number of patients.^{1,8} Second-line treatments include injections and implantable neuromodulation devices.^{1,6,9} There is limited evidence for the effectiveness of these interventions and they can be associated with adverse events such as infection, lead migration, and device failure.^{1,9}

Given the lack of highly effective interventions for CRPS there is a need for better treatment approaches. rTMS is a treatment of interest for several chronic pain conditions that are resistant to other treatment modalities. The mechanism(s) behind the analgesic effects of rTMS are not completely understood but it is thought to include changes in neuronal excitation and increased plasticity.^{10,11} Studies have found rTMS to be an effective intervention for peripheral neuropathy and fibromyalgia.¹¹⁻¹⁶ Most of these studies have only looked at short-term effects but reduced pain up to 4 weeks has been seen.^{11,17} Three studies have investigated the use of rTMS in patients with persistent CRPS symptoms. All three studies found positive short-term

effects with 51-70% of subjects reporting pain relief.¹⁸⁻²⁰ These studies suggest that rTMS may improve the outcomes of patients with CRPS, but the long-term effects are unknown.

In our study, we will look at the combined impact of rTMS and rehabilitation on the outcomes of patients with CRPS. It is hypothesized that rTMS may create a window of reduced pain and increased neural plasticity that magnifies the long-term effects of rehabilitation aimed at cortical reorganization and behavior modification. Graded Motor Imagery (GMI) is a three-part treatment that targets the cortical reorganization that may perpetuate symptoms associated with CRPS.²¹⁻²³ Combining GMI with rTMS may lead to greater changes in cortical reorganization and result in longer-lasting symptoms reduction. Graded exercise and graded activity are common rehabilitation strategies aimed at behavioral changes. By slowly progressing physical activity patients build a “tolerance” that allows them to function at a higher level.²⁴ The pain relief caused by rTMS may help patients better tolerate these graded approaches leading to long-term functional improvement.

3.2 Include complete citations or references:

2. de Mos M, de Bruijn A, Huygen F, Dieleman J, Stricker Bhc, Sturkenboom M. The incidence of complex regional pain syndrome: A population-based study. doi:10.1016/j.pain.2006.09.008
